Attachment 2.	Protocol Addendum RHCD(2.1) Study Design	19

3. Rationale for Addendum

The following addition is being made to Protocol I1F-MC-RHCD (RHCD) for pediatric subjects with plaque psoriasis (Ps). This addendum is to be performed in addition to all procedures required by Protocol RHCD or any subsequent amendments to that protocol.

The following addition will apply in countries where etanercept is approved for severe pediatric psoriasis treatment only (emerging markets and European countries) and where subjects may be randomized to etanercept:

- **Period 2: Double-Blind Treatment Period:** Where applicable, 30 subjects will be randomized to etanercept (Enbrel®), an open-label reference arm. Placebo will not be given to match etanercept. Subjects will only receive placebo to match ixekizumab. To maintain statistical validity, a blinded assessor will conduct the efficacy assessments in countries where etanercept will be administered. Subjects randomized to etanercept during the Double-Blind Treatment Period (Period 2) will begin treatment with ixekizumab during the 48-Week Open-Label Maintenance Period (Period 3) after an 8-week washout period (to avoid increased risks with concurrent etanercept and ixekizumab exposures).

The following addition will also apply for subjects from European (EU) countries:

- **Period 4: 48-Week Double-Blind, Randomized Withdrawal Period:** Subjects from EU countries who meet the response criterion (defined as static Physician's Global Assessment [sPGA] [0,1]) at Week 60 will be rerandomized to ixekizumab or placebo (1:1 ratio). Subjects who are rerandomized to ixekizumab will receive ixekizumab 20, 40, or 80 mg every 4 weeks (Q4W) according to their weight at the time of rerandomization. Upon disease relapse to Ps (sPGA \geq 2), subjects will receive ixekizumab 20, 40, or 80 mg Q4W according to their weight.

The parent or legal guardian will sign the informed consent form (ICF), and the subject will sign the assent form prior to any study assessments, examinations, or procedures being performed.

4. Protocol Additions

The underlined and ~~strike through~~ text in the following sections show the additions and deletions applicable to subjects participating in this addendum. Additionally, the revised Schedule of Activities and study design figure are presented in [Attachment 1](#) and [Attachment 2](#), respectively.

4.1. Use of Etanercept during the Double-Blind Treatment Period (Period 2)

4. Objectives and Endpoints

Objectives	Endpoints
Other Secondary to compare the efficacy of ixekizumab Q4W and etanercept at Week 12 (Visit 7) as measured by PASI 75 and by sPGA (0,1) in countries where etanercept is approved	
 proportion of subjects achieving PASI 75 at Week 12 proportion of subjects achieving sPGA (0,1) at Week 12

Abbreviations: PASI 75 = at least a 75% improvement from baseline in Psoriasis Area and Severity Index score; Q4W = every 4 weeks; sPGA = static Physician's Global Assessment.

5.1. Overall Design

- Period 2: Double-Blind Treatment Period** (Induction Period) will occur from Week 0 (baseline; Visit 2) to Week 12 (Visit 7) comparing ixekizumab to placebo in a double-blind fashion and to etanercept (as a reference arm).
- Period 3: 48-Week Open-Label Maintenance Period** will occur from Week 12 (Visit 7) to Week 60 (Visit 19). Subjects randomized to etanercept during Period 2 will receive ixekizumab at doses of 20, 40, or 80 mg according to their weight after an etanercept 8-week washout period is complete. The etanercept washout period will be from Week 12 through Week 20.
- Period 4: Extension Period** will occur from Week 60 (Visit 19) to Week 108 (Visit 31). Subjects from countries outside of the EU, irrespective of response, and nonresponders from the EU will continue with open-label treatment with the ixekizumab dose received during the previous period (Period 3). Subjects from the EU who meet response criteria (defined as those with sPGA [0,1]) will be rerandomized to ixekizumab or placebo in the Double-Blind, Randomized Withdrawal Period.
(See Section 4.2 of this protocol addendum for details on the Double-Blind, Randomized Withdrawal Period.)

5.1.2. 12-Week Double-Blind Treatment Period (Period 2)

Subjects randomized to etanercept will be administered etanercept 0.8 mg/kg, not exceeding 50 mg per dose, every week from Week 0 through Week 11.

7.1. Treatments Administered

This study involves a comparison of ixekizumab administered by subcutaneous (SC) injection with placebo and with etanercept (as a reference arm). The investigational product (Ixekizumab, etanercept, and placebo) should be at room temperature when injected. Possible injection sites include the abdomen, thigh, and upper arm (using the arm contralateral for blood samples for PK). The injection site should not be in a psoriatic lesion and should be rotated to another area for subsequent doses at the same visit. Placebo will not be given to match etanercept. To maintain statistical validity, a blinded assessor will conduct the efficacy assessments in countries where etanercept will be administered.

After training by the clinical staff, injections of etanercept will be self-administered by the subject or caregiver.

Training: For training purposes, the proper procedures for preparation of the needed dose of etanercept and administration of the initial injection will be performed by clinical staff at Week 0 (Visit 2). Each subject must return to the clinical site for all injections and be trained to self-inject etanercept under the supervision of the investigator until the investigator judges the subject sufficiently competent to perform the self-injections independently. After this time, the subject will be allowed to self-inject at home.

Administration: If the subject is unable to perform the injection, a caregiver may inject etanercept to the subject. In this case, the caregiver will also be trained to inject etanercept to the subject at the study site until the investigator judges the caregiver sufficiently competent to inject. All subsequent injections will be administered by the subject or caregiver.

Table RHCD.3 shows the etanercept treatment regimen.

Table RHCD.3. Etanercept Treatment Regimen

Regimen	Dose Week 0 through Week 11	Week 12 through Week 20
Etanercept	0.8 mg/kg, not exceeding 50 mg per dose	No injections because of the washout period

7.1.1. Packaging and Labeling

Etanercept (Enbrel®) will be supplied by the sponsor or its designee in accordance with cGMP. Etanercept will be supplied in 2 presentations to be administered based on subject weight:

- Powder for solution for injection in a single-dose vial and diluent for reconstitution. Each vial contains 25 mg of etanercept.
- Solution for injection in a single-dose, prefilled, disposable manual syringe. Each syringe of etanercept is designed to deliver 50 mg of etanercept.

7.2. Method of Treatment Assignment

Subjects from countries where etanercept is approved for severe pediatric psoriasis treatment only (emerging markets and European countries) who meet all criteria for enrollment at Visit 1 and Visit 2 will be randomized to double-blind treatment at Week 0 (Visit 2) in a 2:2:1 ratio to ixekizumab, etanercept, or placebo until approximately 75 subjects with severe psoriasis from etanercept-approved countries are randomized to ixekizumab (30 subjects), etanercept (30 subjects), and placebo (15 subjects).

7.3. Blinding

Etanercept will be administered open label during Period 2 and a blinded assessor will be used (see Section 7.1).

7.5. Preparation/Handling/Storage/Accountability

Instructions for the preparation of etanercept will be provided by the sponsor.

7.6. Treatment Compliance

Etanercept: The subject or caregiver will record information in a Study Drug Administration Log, including the date, time, and anatomical location of administration of etanercept (for treatment compliance); carton number; who prepared and administered the investigational product; and the reason if investigational product was not fully administered.

10.3.1. General Statistical Considerations

During the Double-Blind Treatment Period, approximately 75 subjects with severe psoriasis from etanercept-approved countries will be randomized to ixekizumab (30 subjects), etanercept (30 subjects), and placebo (15 subjects) in a 2:2:1 ratio.

Study RHCD (2) will have approximately 85% power to test the superiority of ixekizumab to etanercept for sPGA (0,1) and at least a 75% improvement from baseline in Psoriasis Area and Severity Index score (PASI 75) at Week 12 based on the 2-sided Fisher exact test at significance level of 0.05. The study will have approximately 45% power to test the superiority of etanercept to placebo for PASI 75 at Week 12 based on the 2-sided Fisher exact test at significance level of 0.05. The following assumptions were used for the power calculations for both sPGA (0,1) and PASI 75 response rates based on ixekizumab clinical studies in adult subjects with moderate-to-severe plaque psoriasis (Ps) efficacy data (Griffiths et al. 2015; Gordon et al. 2016): 80% responders for ixekizumab, 40% responders for etanercept, and 10% for placebo.

Subjects with severe psoriasis in countries where etanercept is used as a reference arm will be included in the treatment comparisons of ixekizumab and etanercept for the Double-Blind Treatment Period.

For subjects with severe psoriasis in countries where etanercept is used as a reference arm, treatment comparisons in the proportion of subjects achieving PASI 75 or sPGA (0,1) at Week 12 will be analyzed using Fisher’s exact test. Missing data will be imputed using the nonresponder imputation method (NRI).

Further details will be described in the SAP.

4.2. Double-Blind Randomized Withdrawal Period in Subjects in EU Countries

4. Objectives and Endpoints

Objectives	Endpoints
to assess whether ixekizumab Q4W is superior to placebo for EU subjects during the Double-Blind Randomized Withdrawal Period	
 • time to relapse to moderate severity (sPGA ≥2) during the Double-Blind, Randomized Withdrawal Period • proportion of subjects achieving sPGA (0,1) at Week 108 (Visit 31)

Abbreviations: Q4W = every 4 weeks; sPGA = static Physician’s Global Assessment.

5.1. Overall Design

- **Period 4:**

Extension Period will occur from Week 60 (Visit 19) to Week 108 (Visit 31). Subjects from countries outside of the EU, irrespective of response, and nonresponders from the EU will continue with open-label treatment with the ixekizumab dose received during the previous period.

OR

48-Week Double-Blind, Randomized Withdrawal Period will occur from Week 60 (Visit 19) to Week 108 (Visit 31) for subjects in the EU who meet the response criterion at Week 60 (defined as sPGA [0,1]). Subjects will be rerandomized to ixekizumab or placebo (1:1 ratio).

5.1.4. **48-Week Extension Period or Double-Blind, Randomized Withdrawal Period (Period 4)**

Subjects from EU countries who meet the response criterion at Week 60 (defined as sPGA [0,1]) will be rerandomized to ixekizumab or placebo (1:1 ratio) at Visit 19 (Week 60). Subjects who

are rerandomized to ixekizumab will receive ixekizumab 20, 40, or 80 mg every 4 weeks (Q4W) according to their weight at the time of rerandomization. Upon disease relapse to Ps (sPGA \geq 2), subjects will receive ixekizumab 20, 40, or 80 mg Q4W according to their weight. Subjects from EU countries who do not meet the response criterion at Week 60 will continue with open-label treatment with ixekizumab.

7.2. Method of Treatment Assignment

Subjects who meet response criteria (sPGA [0,1]) from EU countries will enter the Double-Blind Randomized Withdrawal Period and will be rerandomized to double-blind treatment at Week 60 (Visit 19) in a 1:1 ratio to ixekizumab or placebo. Subjects who are rerandomized to ixekizumab will receive ixekizumab 20, 40, or 80 mg Q4W according to their weight at the time of rerandomization. Subjects from EU countries who relapse (sPGA \geq 2) during the Double-Blind Randomized Withdrawal Period will receive open-label treatment with ixekizumab according to their weight at the time of relapse.

7.3. Blinding

During the 48-Week Double-Blind, Randomized Withdrawal Period, subjects from EU countries who meet the response criterion at Week 60 (defined as sPGA [0,1]) will be rerandomized to double-blind ixekizumab or placebo (1:1 ratio).

10.3.1. General Statistical Considerations

During the Double-Blind, Randomized Withdrawal Period (Period 4), approximately 40 subjects from EU countries will be rerandomized to ixekizumab (20 subjects) and placebo (20 subjects) in a 1:1 ratio. The response criterion for rerandomization is sPGA (0,1) at Week 60.

The study will have approximately 95% power to test the superiority of ixekizumab to placebo in time to relapse (sPGA \geq 2) based on the 2-sided log-rank test at a significance level of 0.05. The following assumptions were used for the power calculations: 20% relapse for ixekizumab and 85% relapse for placebo. Relapse rates were estimated based on ixekizumab clinical studies in adult subjects with moderate-to-severe Ps efficacy data (Griffiths et al. 2015; Gordon et al. 2016).

Unless otherwise specified, efficacy, health outcomes, and safety analyses for the Double-Blind, Randomized Withdrawal Period will be conducted on the Double-Blind, Randomized Withdrawal Period Population, defined as all rerandomized patients (i.e., subjects from countries in the EU who were rerandomized at Week 60) who received at least 1 dose of study treatment during Double-Blind, Randomized Withdrawal Period. Patients will be analyzed according to the treatment to which they were rerandomized.

Treatment comparisons of ixekizumab and placebo during the Double-Blind, Randomized Withdrawal Period will be performed for the Double-Blind, Randomized Withdrawal Period Population.

The time to relapse (loss of response; sPGA ≥ 2) during Double-Blind, Randomized Withdrawal Period (Period 4) is defined as:

$$\textit{Time to relapse (days)} = \textit{date of first sPGA} \geq 2 \textit{ during Period 4} - \textit{date of Week 60 rerandomization} + 1.$$

If a patient has not experienced relapse (sPGA ≥ 2) by completion or early discontinuation of Period 4, the patient will be censored at the date of their last visit during Period 4.

The number of patients at risk and experiencing a relapse event by each scheduled visit during Period 4 will be presented by treatment group. The Kaplan–Meier estimate of the proportion of patients relapsing will be presented for each visit. Treatment group comparisons will be performed using the log-rank test. For each treatment group, a Kaplan–Meier plot of the time to relapse will be provided.

Treatment comparisons in the proportion of subjects achieving sPGA (0,1) at Week 108 will be analyzed using Fisher’s exact test. Missing data will be imputed using the NRI.

Further details will be described in the SAP.

5. References

**Attachment 1. Protocol Addendum RHCD(2.1)
Schedule of Activities**

Schedule of Activities, Protocol I1F-MC-RHCD(2.1)
 Screening (Period 1) and Double-Blind Treatment Period (Period 2)

	Screening (Period 1)	Double-Blind Treatment Period (Period 2)					
		Randomization					
Visit No (V)	V1	V2	V3			V4	
Study Week		W0	W1	W2	W3	W4	W5
Study Days (Approximately)	-30 to -7 d	0	7 ± 2d	14 ± 2d	21 ± 2d	28 ± 2d	35 ± 2d
Informed consent and assent ^a	X						
Randomization		X					
Dispense study drug ⁱ		X	X			X	
Administer study drug ^{j,k}		Group 1: IXE 40, 80, or 160 mg or placebo Group 2: etanercept	Group 1: no injections Group 2: etanercept	Group 1: no injections Group 2: etanercept	Group 1: no injections Group 2: etanercept	Group 1: IXE 20, 40, or 80 mg or placebo Group 2: etanercept	Group 1: no injections Group 2: etanercept

Schedule of Activities, Protocol I1F-MC-RHCD(2.1)
 Double-Blind Treatment Period (Period 2)

	Double-Blind Treatment Period (Period 2)						
Visit No (V)	V5		V6				V7
Study Week	W6	W7	W8	W9	W10	W11	W12
Study Days (Approximately)	42 ± 2d	49 ± 2d	56 ± 2d	63 ± 2d	70 ± 2d	77 ± 2d	84 ± 2d
Dispense IP ⁱ	X		X				
Administer IP ^{j,k}	Group 1: no injections Group 2: etanercept	Group 1: no injections Group 2: etanercept	Group 1: IXE 20, 40, or 80 mg or placebo Group 2: etanercept	Group 1: no injections Group 2: etanercept	Group 1: no injections Group 2: etanercept	Group 1: no injections Group 2: etanercept	Group 1: IXE 20, 40, 80, or 160 mg or placebo Group 2: no injections

Schedule of Activities, Protocol I1F-MC-RHCD(2.1)
Maintenance Period (Period 3)

Maintenance Period (Period 3)							
Visit No (V)	V8	V9	V10	V11	V12	V13	V14
Study Week	W16	W20	W24	W28	W32	W36	W40
Study Days (Approximately)	112 ± 7d	140 ± 7d	168± 7d	196± 7d	224± 7d	252± 7d	280± 7d
Dispense IP ⁱ	X	X	X	X	X	X	X
Administer IP	
Group 1: IXE 20, 40, or 80 mg
 
Group 2: no injections
	
Group 1: IXE 20, 40, or 80 mg
 
Group 2: IXE 40, 80, or 160 mg
	
All subjects: IXE 20, 40, or 80 mg
				

Schedule of Activities, Protocol I1F-MC-RHCD(2.1)

Maintenance Period (Period 3) and Extension Period or Double-Blind, Randomized Withdrawal Period (Period 4)

	Maintenance Period (Period 3)					Extension Period or Double-Blind, Randomized Withdrawal Period (Period 4)								
	V15	V16	V17	V18	V19	V20	V21	V22	V23	V24	V25	V26	V27	V28
Visit No (V)	V15	V16	V17	V18	V19	V20	V21	V22	V23	V24	V25	V26	V27	V28
Study Week	W44	W48	W52	W56	W60	W64	W68	W72	W76	W80	W84	W88	W92	W96
Study Days (Approximately)	308 ± 7d	336 ± 7d	364 ± 7d	392 ± 7d	420 ± 7d	448 ± 7d	476 ± 7d	504 ± 7d	532 ± 7d	560 ± 7d	588 ± 7d	616 ± 7d	644 ± 7d	672 ± 7d
Randomization					X									
Dispense IP ⁱ	X	X	X	X	X	X	X	X	X	X	X	X	X	X
Administer IP	All subjects: IXE 20, 40, or 80 mg					Group 1 (EU nonresponders and all OEU subjects): Open-label IXE 20, 40, or 80 mg ^w Group 2 (responders from EU countries): Double-blind IXE 20, 40, or 80 mg or placebo ^w								

Schedule of Activities, Protocol I1F-MC-RHCD(2.1)
 Extension Period (Period 4) and Post-Treatment Follow-Up (Period 5)

	Extension Period (Period 4)			Post-Treatment Follow-Up Period (Period 5) ^v		
	V29	V30	V31/ ETV	V801	V802	V803 ^w
Visit No (V)	V29	V30	V31/ ETV	V801	V802	V803 ^w
Study Week	W100	W104	W108	LV + 4W	LV + 12W	LV + 24W
Study Days (Approximately)	700 ± 7d	728 ± 7d	756 ± 7d	± 4d	± 4d	± 4d
Telephone Visit	✕	✕				
Dispense IP ⁱ	X	X				
Administer IP	Group 1 (nonresponders and OEU subjects): Open-label IXE 20, 40, or 80 mg ^w Group 2 (responders from EU countries): Double-blind IXE 20, 40, 80 mg or placebo ^w					

[figure not shown]
Schedule of Activities, Protocol I1F-MC-RHCD(2.1)

Abbreviations: d = day; ETV = early termination visit; EU = European Union; IP = investigational product; IXE = ixekizumab; LV= date of last visit; OEU = outside the European Union; V = study visit; W = study week.

- a The parent or legal guardian will sign the informed consent form (ICF), and the subject will sign the assent form prior to any study assessments, examinations, or procedures being performed. An ICF should be signed by the subject when the legal age is reached as determined by the country regulations.
- i For training purposes, the proper procedures for preparation of needed dose of etanercept and administration of the initial injection will be performed by clinical staff at Week 0 (Visit 2). Each subject must return to the clinical site for all injections and be trained to self-inject etanercept under the supervision of the investigator until the investigator judges the subject sufficiently competent to perform the self-injections independently. After this time, the subject will be allowed to self-inject at home. If the subject is unable to perform the injection, a caregiver may inject etanercept to the subject. In this case, the caregiver will also be trained to inject etanercept to the subject at the study site until the investigator judges the caregiver sufficiently competent to inject. All subsequent injections will be administered by the subject or caregiver. The subject or the caregiver will record information in the Study Drug Administration Log, including the date, time, and anatomical location of administration of IP (for treatment compliance); carton number; who administered the IP; and the reason if IP was not fully administered.
- k **Group 1:** Subjects receiving ixekizumab 20 mg or 40 mg will receive 1 SC injection of ixekizumab at Week 0 (Visit 2) and 1 SC injection of ixekizumab Q4W at Weeks 4 and 8. Subjects receiving ixekizumab 80 mg will receive 2 SC injections of ixekizumab at Week 0 (Visit 2) and 1 SC injection of ixekizumab Q4W at Weeks 4 and 8.
Subjects receiving placebo for ixekizumab 20 mg or 40 mg will receive 1 SC injection of placebo at Week 0 (Visit 2) and 1 SC injection of placebo Q4W at Weeks 4 and 8. Subjects receiving placebo for ixekizumab 80 mg will receive 2 SC injections of placebo at Week 0 (Visit 2) and 1 SC injection of placebo Q4W at Weeks 4 and 8.
Group 2: Subjects randomized to etanercept will receive etanercept every week (Q1W) at Week 0 through Week 11. After training by the clinical staff, injections of etanercept will be self-administered by the subject or caregiver, as described in Section 7.1.
- u All subjects receiving IP must enter into the Post-Treatment Follow-Up Period (Period 5) and complete through Visit 802. Subjects may be followed beyond Visit 802 for continued monitoring of their neutrophil counts. If a subject discontinues IP early, the subject will complete the ETV and then enter the Post-Treatment Follow-Up Period (Period 5).
- v This visit will only occur if a subject's neutrophil counts have not returned to the defined criteria.
- w **Group 1:** All subjects from non-EU countries and nonresponders from EU countries will receive 1 SC injection of ixekizumab Q4W.
Group 2: Responders from EU countries will be rerandomized to either ixekizumab or placebo. Subjects will receive 1 SC injection Q4W. Subjects on placebo will receive ixekizumab upon disease relapse to psoriasis (sPGA \geq 2).

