5.2. Determination of Sample Size

5.2.1. Clinical Protocol RHCD

Sample size of this study is based on the regulatory requirements from the European Medicine's Agency Paediatric Investigation Plan for ixekizumab. The regulatory requirements for the number of subjects in each treatment group were: (1) at least 170 randomized subjects (at least 90 to ixekizumab, at least 25 to etanercept, and at least 55 to placebo); and (2) at least 30% of subjects from the EU.

In the main protocol RHCD, approximately 165 subjects will be randomized in a 2:1 ratio to receive ixekizumab (110 subjects) or placebo (55 subjects) during the Double-Blind Treatment Period. The study will have >99% power to test the superiority of ixekizumab to placebo for PASI 75 and for sPGA (0,1) at Week 12, based on the 2-sided Fisher's exact test at a significance level of 0.05. The following assumptions were used for the power calculations for both sPGA (0,1) and PASI 75 responses rates, based on ixekizumab clinical studies in adult subjects with moderate-to-severe Ps efficacy data (Griffiths et al. 2015; Gordon et al. 2016): 80% response for ixekizumab and 10% response for placebo for both PASI 75 and sPGA (0,1).

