5.3.2. Protocol Addendum RHCD(2)

Subjects from countries where etanercept is approved for severe pediatric Ps treatment only who meet all criteria for enrollment at Visit 1 and Visit 2 will be randomized to double-blind treatment at Week 0 (Visit 2) in a 2:2:1 ratio to ixekizumab, etanercept, or placebo.

Subjects who meet response criteria (sPGA 0,1) from EU countries will enter the Double-Blind Randomized Withdrawal Period and will be re-randomized to double-blind treatment at Week 60 (Visit 19) in a 1:1 ratio to ixekizumab or placebo. Subjects who are re-randomized to ixekizumab will receive ixekizumab 20, 40, or 80 mg every 4 weeks (Q4W) according to their weight at the time of re-randomization. Subjects from EU countries who relapse (sPGA ≥ 2) during the Double-Blind Randomized Withdrawal Period will receive open-label treatment with ixekizumab according to their weight at the time of relapse.

6. A Priori Statistical Methods

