Intent-to-Treat (ITT) – Etanercept Approved Countries (per Protocol Addendum[2])	Double-Blind Treatment Period (Period 2)	All randomized subjects per Protocol Addendum(2) in etanercept-approved countries (that is, subjects with severe psoriasis in countries where etanercept is used as a reference arm), even if the subject does not take the assigned treatment, does not receive the correct treatment, or, otherwise, does not follow the protocol. Subjects will be analyzed according to the treatment to which they were assigned.
Per-Protocol Set (per main study)	Double-Blind Treatment Period (Period 2)	All randomized subjects who do not have significant protocol violations (refer to Section 6.16). Subjects will be analyzed according to the treatment to which they were assigned. .
Safety Population (per main study)	Double-Blind Treatment Period (Period 2)	All randomized subjects who take at least 1 dose of double-blind study treatment. Subjects will be analyzed according to the treatment to which they were assigned.

Population	Period	Description
Safety Population – Etanercept-Approved Countries (per Protocol Addendum[2])	Double-Blind Treatment Period (Period 2) per Protocol Addendum(2)	All randomized subjects in Protocol Addendum(2) in etanercept countries who take at least 1 dose of double-blind study treatment per Protocol Addendum(2). Subjects will be analyzed according to the treatment to which they were assigned.
Double-Blind, Randomized Withdrawal Period Population	Randomized-Withdrawal Period (Period 4) per Protocol Addendum(2)	All re-randomized patients (that is, subjects from countries in the EU who were re-randomized at Week 60) who received at least 1 dose of study treatment during Double-Blind, Randomized Withdrawal Period.
Ixekizumab Efficacy Primary Population	Combined Treatment Periods (Periods 2, 3, and 4)	All subjects randomized to ixekizumab at Week 0 (Visit 2) and who received ixekizumab throughout their study participations. The following subjects are not included in this analysis population: (1) patients randomized to etanercept or placebo at Week 0; and (2) patients who are re-randomized to placebo during Period 4 per Protocol Addendum(2).

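### The Week 108 sPGA (0,1) comparison in Period 4 counts placebo subjects who relapse and recover on open-label ixekizumab as placebo responders

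*Protocol*

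**What the plan says.** In Period 4, about 40 EU subjects with sPGA (0,1) at Week 60 are rerandomized 1:1 to ixekizumab or placebo. The objective in Section 4.2 of the protocol addendum is "to assess whether ixekizumab Q4W is superior to placebo for EU subjects during the Double-Blind Randomized Withdrawal Period". It has two endpoints: time to relapse (sPGA 2 or more) and the proportion with sPGA (0,1) at Week 108. SAP Table RHCD.4.2 repeats both.

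Four provisions decide how a relapsed subject counts at Week 108:

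- **Treatment after relapse.** Section 7.2 of the addendum says EU subjects who relapse in this period "will receive open-label treatment with ixekizumab according to their weight at the time of relapse". SAP Section 5.3.2 says the same.
- **Analysis group.** Section 10.3.1 of the addendum: "Patients will be analyzed according to the treatment to which they were rerandomized".
- **Test.** Section 10.3.1 again: "Treatment comparisons in the proportion of subjects achieving sPGA (0,1) at Week 108 will be analyzed using" Fisher's exact test, with NRI for missing data. Further detail is left to the SAP.
- **Nonresponse.** Under SAP Section 6.3.1 a subject is a nonresponder when the response criterion is not met or the data are missing at the analysis time point. Relapse and change of treatment are not mentioned.

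SAP Section 6.1.3.4, Table RHCD.6.4 and Section 6.11.4 add no exception for Period 4. Section 6.1.2 acknowledges rescue with ixekizumab after relapse, but only to set a safety baseline.

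**The concern.** Taken together, these provisions count a placebo subject who relapsed, restarted ixekizumab and regained sPGA 0 or 1 by Week 108 as a success for placebo. The value is observed, so NRI does not act on it. On the plan's 85% placebo relapse rate, about 17 of 20 placebo subjects could be on ixekizumab at some point before Week 108.

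Elsewhere the SAP keeps these data apart. In Table RHCD.6.1 the Ixekizumab Efficacy Primary Population leaves out subjects rerandomized to placebo, and the Secondary Population leaves out their Period 4 data. Their response after retreatment is therefore in no ixekizumab efficacy population and enters Period 4 efficacy only under the placebo label. Neither document declares a treatment-policy intent.

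A named endpoint of a superiority objective would thus be pulled toward no difference by the effect of the test drug itself, and a null result could not be interpreted. The same gap reaches the other visit-wise sPGA and PASI responder tests in Period 4. The effect is smaller at early visits, when few subjects can have relapsed and recovered.

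**Working it through.** **Inputs.** From addendum Section 10.3.1 and SAP Section 5.2.2: 20 subjects per arm; relapse 20% on ixekizumab and 85% on placebo; 2-sided 0.05; about 95% log-rank power for time to relapse. No power is stated for the Week 108 test. Assumed here: the relapse rates are cumulative to Week 108 and there is no dropout. The share of relapsers who recover is not in the documents, so it is varied.

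**The plan's own figure.** Hazard ratio = ln(0.80)/ln(0.15) = 0.1176. Expected events = 20×0.20 + 20×0.85 = 21. Freedman's formula: Φ(√21 × (1 − 0.1176)/(1 + 0.1176) − 1.96) = Φ(3.618 − 1.96) = 95.1%. The stated 95% is reproduced. It uses the first sPGA of 2 or more, so retreatment cannot change it.

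**Week 108 response as written.** With recovery shares rI (ixekizumab) and rP (placebo):

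- ixekizumab response = 0.80 + 0.20 rI
- placebo response = 0.15 + 0.85 rP
- difference = 0.65 + 0.20 rI − 0.85 rP

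The difference falls below 0.65 whenever rP > (0.20/0.85) rI = 0.235 rI.

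**Equal recovery in both arms.** Exact 2-sided Fisher power, by enumerating both binomials:

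| r | Ixekizumab | Placebo | Power |
|---|---|---|---|
| 0 (relapse = nonresponse) | 80% | 15% | 98.7% |
| 0.2 | 84% | 32% | 89% |
| 0.4 | 88% | 49% | 70% |
| 0.5 | 90% | 57.5% | 56% |
| 0.6 | 92% | 66% | 42% |
| 0.8 | 96% | 83% | 12% |

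**No recovery in the ixekizumab arm.** At rP = 0.5 the rates are 80% and 57.5%, and power is 24%. The arms are equal at rP = 0.65/0.85 = 76.5%, and placebo is ahead above that.

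**Allowing for timing.** Late relapsers have little time to recover. Assume constant hazards over 48 weeks: −ln(0.15)/48 = 0.0395 per week on placebo and −ln(0.80)/48 = 0.00465 on ixekizumab. The share of relapses at least L weeks before Week 108 is (1 − exp(−h(48 − L))) divided by the cumulative relapse rate. A share q of these early enough relapsers recovers.

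| Lag L | Early enough, placebo / ixekizumab | q = 0.2 | q = 0.4 | q = 0.6 | q = 0.8 |
|---|---|---|---|---|---|
| 12 weeks | 89% / 77% | 90% | 72% | 45% | 19% |
| 24 weeks | 72% / 53% | 92% | 79% | 57% | 33% |

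The only ixekizumab response figure in the documents is the 80% Week 12 planning rate (SAP Sections 5.2.1 and 5.2.2). It concerns initial treatment, not recovery after relapse, so q = 0.8 is a reference point and not an estimate.

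**The case against.** The strongest reply is that the text does settle the matter: as-rerandomized grouping with observed values is one determinate analysis, and it answers a legitimate question about withdrawal with retreatment available. Time to relapse already answers the pure withdrawal question and carries the stated power. If relapse counted as permanent nonresponse, Week 108 would largely repeat it. An ixekizumab-arm subject who relapses and recovers is also still responding on the randomized drug, so permanent nonresponse looks harsh there. Finally, the size rests on a recovery share that nobody has given.

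Part of this stands. The endpoint is other secondary without multiplicity adjustment, the distortion usually works against ixekizumab, and the overlap with time to relapse is a real cost. The power figures illustrate a mechanism only. The main protocol was not among the documents, so the absence of a rule is shown for the addendum and the SAP.

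The defect remains. Neither document says the retreatment question is intended, and the stated objective is superiority over placebo during withdrawal. Following the stated rule yields a diluted comparison, so this is more than missing detail. Applying nonresponse after relapse to both arms is deliberate: a placebo-only rule would treat the same event differently by arm.

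**Conclusion.** The concern holds. As written, the Week 108 sPGA (0,1) test credits placebo with responses regained on ixekizumab. On the plan's relapse rates, Fisher power falls from 98.7% with relapse as nonresponse to 56% with 50% recovery and 12% with 80% recovery, equal in both arms. With a recovery lag of 12 or 24 weeks and 80% recovery among early enough relapsers it is 19% or 33%. These figures assume cumulative rates, no dropout, equal recovery shares in the two arms and, for the lag cases, constant hazards. The direction needs only that placebo recovery exceed 0.235 times ixekizumab recovery. The point should be fixed, but it does not touch time to relapse, the co-primary endpoints or the gated tests.

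**What to change.** The change is to the analysis only. In SAP Sections 6.3.1 and 6.1.3.4 and Table RHCD.6.4, state for the Randomized Withdrawal Period Population:

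- **sPGA (0,1) and sPGA (0):** subjects in both arms are nonresponders from their first sPGA of 2 or more onward.
- **PASI responder endpoints:** subjects are nonresponders at visits after open-label retreatment starts, and the PASI at the relapse visit is kept as observed. The rule differs because sPGA 2 is graded mild (Table RHCD.6.3) and PASI response is measured from Week 0 (Section 6.1.2), so a subject can relapse on sPGA while still a PASI responder on randomized treatment.

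Name NRI in the Period 4 PASI row of Table RHCD.6.4, which lists Fisher's exact test alone and is covered only by the general text of Section 6.3.1. Keep the as-observed, as-rerandomized comparison as supportive, and summarise response after retreatment separately.

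The scope of retreatment must also be reconciled. Footnote w in Attachment 1 of the addendum says "Subjects on placebo will receive ixekizumab upon disease relapse to psoriasis", whereas addendum Section 7.2 and SAP Section 5.3.2 cover all relapsed subjects. On the narrower reading the PASI rule would act in one arm only.

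The cost is two SAP rules with the matching table edits, one supportive analysis, one summary and two dates. The first sPGA of 2 or more is already derived for time to relapse. For placebo subjects the retreatment start is already needed for the second-exposure safety baseline; for ixekizumab-arm subjects it should come from dispensing or exposure data. The price is that, with little dropout, Week 108 sPGA (0,1) will largely mirror one minus cumulative relapse.
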